Primary outcomes: Increased peak isokinetic muscle torque output as measured using a Biodek machine of the shoulder internal rotators, external rotators, shoulder abductor/adductors, and shoulder flexion/extension, elbow flexion/extension, forearm pronation/supination, wrist flexion/extension, and hand grip measured using a handheld dynamometer at 6 weeks (mid-way into training) and 12 weeks (end of training) when compared to baseline.

Secondary outcomes:

- o Propulsion testing: Increased maximum speed and acceleration attained, peak force, and mechanical effective force measured using the SmartWheel during start-up propulsion over level and inclined surfaces at 12 weeks when compared to baseline
- o Transfer testing: Higher maximum and minimum attainable transfer heights to a height-adjustable transfer station at 12 weeks when compared to baseline;
- o Reduced upper limb pain across all joints (as recorded on the Numerical Rating Scale (NRS) and shoulder pain reported during activities (Wheelchair Users Shoulder Pain Index (WUSPI)) at 6 weeks and 12 weeks when compared to baseline;
- o Increased self-perceived aspects of health and function as measured using the Short Form SF-36 Walk Wheel scale at 6 weeks and 12 weeks and when compared to baseline.
- o Increased peak power and average power output at 12 weeks compared to baseline.

Specific Aim 2) Assess subjects' perceptions of the effectiveness of the vibration dumbbell training program

Hypothesis 2) Subjects will report a high level of satisfaction with the training on factors of efficiency, tolerance, perceived strength and functional benefits.

Study Design and Methods

Each subject will be asked to come to HERL three times over a 12-week study period. During these visits the following activities will take place a) Pain and Health Surveys (Baseline and Weeks 6, and 12), b) Muscle Strength Testing (Baseline and Weeks 6 and 12), c) Functional Testing (Baseline and Week 12), and Pre-Training Assessment and Instructions (Baseline). The 12-week Training Phase will start after Visit 1

Data will be collected electronically using redcap, or on paper as needed.

Visit 1 (Initial Visit)

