Training intensity will be adjusted progressively with add-on dumbbell weights that will be added to the vibrating dumbbell. Subjects will be asked to hold onto the vibrating dumbbell tightly for as long as they can for each exercise. If they are unable to hold on tightly for at least 15 seconds, the weight for the next session will be decreased, whereas if they are able to hold onto the dumbbell for greater than 60 seconds, the trainer will stop the exercise and the dumbbell weight will be increased for the next session. The amount of weight increased and decreased will be determined by the trainer and will be reviewed and verified by a member of the senior study personnel.

The trainer will meet with the senior study personnel (PT and PI) at minimum once a week to review subjects' training progress, performance, any complications, concerns or complaints that the subject expresses, and any changes in the health status of the subjects who had been seen over the course of the week. Senior personnel will re-assess and modify the training procedures as appropriate.

During the last week of training (week 12), the trainer will give subjects a survey to assess satisfaction with the training program to collect their feedback on factors such as tolerance, perceived strength, performance and health benefits, efficiency of training, choice to continue training, and if they would recommend this form of exercise to others.

The follow-up outcome assessment visit, which take place at our laboratory, will be conducted by the PhD student and overseen by the PI.

Visit 2 (midway visit)

Participants will come back to the lab 6-8 weeks from the beginning of the intervention. The follow-up visit intake form will be completed to identify any changes in the participants health or medical status, lifestyle or any other changes that could impact the participants ability to complete the exercise program. At this visit we will test their strength in the same way that it was tested on initial visit. Additionally, they will fill out the pain measure forms, the health and satisfaction form and the carpal tunnel questionnaire that were filled out at the first visit.

This visit is expected to take no more than 2 hours to complete.

Visit 3 (end of the exercise program)

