At the end of the 12-week intervention period, subjects will come back to the lab for the final visit. This visit will be scheduled 12-14 weeks after the start of the intervention. However, even if a participant is unable to come back at 12 weeks exactly, the exercise program will still end at 12 weeks.

The follow-up visit intake form will be completed to identify any changes in the participants health or medical status, lifestyle or any other changes that could impact the participants ability to complete the exercise program. At this visit subjects will complete all the measures that were completed during the first visit. This includes the pain measures, measure of health and function, carpal tunnel questionnaire, strength, power output and functional measures. These tasks are expected to take up to 5 hours to complete.

As stated above, three exercise sessions will be scheduled each week. We expect that this schedule will be modified due to scheduling conflicts, illness, etc. and it is possible that subjects may sometimes complete less than three visits per week. All visits that are changed or missed will be documented in the research record but will not be considered protocol deviations so long as they are completing a minimal number of sessions (10) per six-week period. If a subject completes less than 10 exercise sessions in a 6-week period they will be removed from the study.

As stated above, testing sessions at the HERL lab will be scheduled at 6 and 12 weeks from the baseline visit. We expect that this schedule will be modified due to scheduling conflicts, illness, etc. For this reason, subjects will be given a 2-week window (6-8, 12-14 weeks) in which to complete these visits. Testing sessions within this window will not be considered protocol deviations.

Eligibility Criteria

Inclusion Criteria:

- (1) have a neurological impairment secondary to a SCI or disease at T2 or lower
- (2) greater than 6 months post injury
- (3) use a manual wheelchair as primary means of mobility (at least 30 hrs. per week)
- (4) 18 to 65 years of age
- (5) provide signed medical release by primary care physician to engage in a high-intensity resistance training exercise program
- (6) live within 60 minutes driving time (1 hour) from the research center
- (7) able to perform a transfer independently to and from a wheelchair
- (8) have normal range of motion in the upper limbs.

Exclusion Criteria:

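### Subjects below the session minimum are removed from the study with no provision for assessing them afterwards, so week-12 results may describe adequate attenders only

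*Combined protocol and SAP*

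**What the plan says.** Training is planned at three sessions a week for 12 weeks. The schedule rules under Visit 3 expect some sessions to be moved or missed. These are recorded and do not count as deviations "so long as they are completing a minimal number of sessions (10) per six-week period". Below that, "If a subject completes less than 10 exercise sessions in a 6-week period they will be removed from the study". The text does not say when removal takes effect.

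The assessments fall at or after the close of each six weeks of training:

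- Visit 2: "Participants will come back to the lab 6-8 weeks from the beginning of the intervention".
- Visit 3: "This visit will be scheduled 12-14 weeks after the start of the intervention".
- Strength, pain and the SF-36 are measured at baseline, week 6 and week 12. Propulsion and transfers are measured only at baseline and week 12 (Study Design and Methods). Power likewise: "Increased peak power and average power output at 12 weeks compared to baseline".
- For Aim 2, Training Intensity Assessment and Adjustments says: "During the last week of training (week 12), the trainer will give subjects a survey to assess satisfaction with the training program".

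The Statistical Plan specifies a repeated measures ANCOVA, with the number of sessions completed as a covariate if needed. It names no analysis set, no missing-data method and no sensitivity analysis. No section describes an early-termination visit or continued assessment.

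**The concern.** Attendance arises after enrolment and may be affected by the training itself. If removal ends assessment, the week-12 strength, pain, SF-36, power, propulsion and transfer results come only from subjects who met the minimum. Hypothesis 1 is a change from baseline. The training description mentions a control and a vibration group, but the Statistical Plan sets out no between-group comparison, so no comparator would offset selective loss.

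If low attenders tend to have more pain, a poorer response or less liking for the programme, both the mean change and the satisfaction results will look too good. A link with pain is possible, because training stops when a subject reports pain and resumes only after contact with a physician. That is an inference: the reasons the plan gives for changed or missed sessions are scheduling clashes, illness and an unspecified remainder.

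**Working it through.** The plan states no attendance rate, dropout rate or sample size, so there is no figure to reproduce. The check has two parts: who loses which data, and how large the effect could be under stated assumptions.

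**Who loses what, if removal ends assessment**

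- Scheduled sessions: 3 × 6 = 18 per six weeks and 3 × 12 = 36 in all. Threshold: 10/18 = 55.6%. Removal needs at least 9 misses out of 18. A subject retained throughout has at least 10 + 10 = 20 of 36 sessions.
- Short in weeks 1-6: no week-12 data. Visit 2, at 6-8 weeks, may be lost too, which would leave no post-baseline strength value.
- Short only in weeks 7-12: visit 3 is lost, but week-6 strength, pain and SF-36 may exist. There is no post-baseline function or power.
- Aim 2: a subject who leaves before week 12 is never given the training survey. One who falls short only at the end of week 12 may already have answered. Visit 2 does repeat "the health and satisfaction form and the carpal tunnel questionnaire that were filled out at the first visit", but a form first completed before training cannot be the rating of the training.

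**Share removed (attendance rates assumed)**

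Take fixed blocks (weeks 1-6 and 7-12), independent sessions and a common attendance rate q. For one block, p = P(Bin(18, q) ≤ 9). For either block, P = 1 − (1 − p)².

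| q | p | P |
|---|---|---|
| 0.80 | 0.0043 | 0.0085 |
| 0.75 | 0.0193 | 0.0383 |
| 0.70 | 0.0596 | 0.1156 |
| 0.65 | 0.1391 | 0.2588 |

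If each subject has a personal rate drawn from a beta distribution (assumed intraclass correlation 0.1 or 0.2), P is 0.098 or 0.153 at a mean of 0.80, and 0.254 or 0.295 at a mean of 0.70.

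If the six weeks were a rolling window (seven windows, ending in weeks 6 to 12), the independent-session figures would be 1.8, 7.2, 19.0 and 37.1% at 80, 75, 70 and 65%.

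**Effect on the mean change**

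Let retained subjects gain G on average and removed subjects rG. The all-enrolled mean is (1 − P)G + PrG, so retained mean ÷ all-enrolled mean = 1/(1 − P + rP).

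| r | P = 0.1 | P = 0.2 | P = 0.3 |
|---|---|---|---|
| 0 | 1.11 | 1.25 | 1.43 |
| 0.5 | 1.05 | 1.11 | 1.18 |
| 1 | 1.00 | 1.00 | 1.00 |
| 1.25 | 0.98 | 0.95 | 0.93 |

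At 80% attendance with independent sessions, even r = 0 gives only 1/(1 − 0.0085) = 1.009, or 1.018 with rolling windows.

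**Does the session-count covariate help?** No. It is optional, it spans only 20 to 36 sessions among retained subjects, and it cannot restore outcomes that were never collected.

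**The case against.** The study is exploratory, and the effect in people who train adequately is a legitimate target. The threshold is lenient. The trainer travels to the subject's home or another convenient place and the schedule is flexible, so attendance may be good and removals few. Asking people who have stopped to return for a visit of up to five hours may yield little. Missed sessions are documented.

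Much of this stands. It limits the size of the problem, and at high, uniform attendance the effect is negligible. But the plan does not say that adequate attenders are its target or that removals will be reported, and a record of missed sessions is not an outcome. Assessing everyone still allows the adequate-attender analysis; removal rules out the wider one.

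A reader might infer more than the documents support:

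- *That week-12 results are certainly restricted.* The text provides for no later assessment, but does not forbid it. Ending assessment is the ordinary reading, not an explicit statement.
- *That results are biased upwards.* Selection on attendance is not bias in itself. If attendance is unrelated to response, the mean is unbiased; if removed subjects would have gained more, the bias is downwards.
- *That rolling windows apply.* With a 12-week programme tested at weeks 6 and 12, fixed blocks are the more natural reading. The rolling figures show only that the wording matters.
- *That a loss rate for the Aim 2 survey can be calculated.* It depends on when removal takes effect, which is not stated.

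**Conclusion.** The point holds in conditional form and should be fixed. As written, the rule takes low attenders out of the study, and in its ordinary sense it leaves week-12 results, and the only survey of satisfaction with the training, to those who met the minimum. The loss is most complete for function and power, which have no earlier post-baseline measurement.

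The size is unknown. On assumed attendance of 65-80% with fixed blocks and independent sessions, removal runs from under 1% to about 26%. It is about 10-15% at a mean of 80% if attendance differs between subjects to the degree assumed. An overstatement of 1.05-1.43 times requires both 10-30% removed and removed subjects gaining nothing to half as much. Neither input comes from the documents. Confidence is high on the text and moderate on its importance.

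**What to change.** - Separate stopping training from leaving the study. The rule for stopping training stays with the protocol.
- Invite subjects below the minimum, where they are willing and it is safe, to the existing week-6 and week-12 assessments, at least the pain and health surveys.
- Give the satisfaction survey when a subject stops training, as well as in week 12.
- State whether the six weeks are a fixed block or a rolling window, and when the rule takes effect.
- Analyse all enrolled subjects with a baseline, using all available visits and a method that does not drop a subject for one missing visit, such as a linear mixed model. For function and power this recovers little unless week 12 is collected, so continued assessment matters most there.
- Show subjects who met the minimum as a sensitivity analysis, and report the number removed with week and reason.

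The cost is a short amendment and some added SAP wording; the visits, surveys and data capture already exist. Against that, early stoppers must be asked back and may decline visits of up to two and five hours, and the mean gain may look smaller.

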training upper limb muscle force and power. For any subject who begins training at 30 Hz, the frequency will be reassessed at each training session to progressively increase him/her (in increments of 5 Hz) to 40 Hz.

The vibrating dumbbell, without added weights, weighs 6 pounds. It is possible that early in the exercise program a subject in the vibration intervention group may not be able to properly perform a specific exercise with that weight. In this case the subject will perform the exercise with a lighter weight standard dumbbell until they increase sufficiently in strength.

Visit 1 will take up to 5 hours to complete.

Optimally, each subject will be scheduled for three training sessions per week in their home for 12 consecutive weeks. Although the home was chosen for the training setting to make it easier on subjects to comply with the protocol, training can take place in another location based on subject convenience. The training equipment is portable and can be easily setup and broken down after each session. All the training for both the control and vibration groups will be supervised by a trainer with appropriate knowledge of proper exercise form and safety. The trainer will travel to the agreed upon location and guide the subject through each training session. The training sessions will be monitored by a physical therapist (PT). Both the trainer and PT will be masked to subjects' performance on outcome measurements.

Prior to beginning each exercise session, female subjects will be reminded that they should not participate in vibration exercise activities if they are pregnant and should notify the study team if they think they could be. Female subjects will be asked weekly if they are or could be pregnant and this will be documented. If pregnancy is a possibility, the subject will be offered an over the counter pregnancy test. Subjects will be given the test to perform themselves, unless they are physically unable to because of disability related functional limitations. In these circumstances, a female staff member will assist as needed. Any subject reporting or testing positive for pregnancy will be withdrawn from the study.

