- (1) history of fractures or dislocations in the shoulder, elbow and wrist from which the subject has not fully recovered or joint replacement of any of the joints in the upper extremities
- (2) upper limb pain that interferes with the ability to propel or transfer
- (3) recent hospitalization for any reason (within the past three months)
- (4) pregnant women
- (5) history of coronary artery disease, coronary bypass surgery or other cardiorespiratory events

Statistical Plan

Distributions of all data will be examined. Should outliers or distributions that are nonlinear in nature be present, appropriate transformations will be performed. Means and standard deviations, or medians and ranges, as appropriate, will be calculated for all variables. A repeated measures ANCOVA will be used to examine primary (strength) and secondary outcome measures (pain, quality of life, power, transfer ability, propulsion characteristic) for the three time points. For significant models, post-hoc analyses with Bonferroni corrections will be used. Total number of training sessions completed will be entered as a covariate if necessary. The training progress (e.g. hold times) and training adaptations made and documented by the trainer during each session will be analyzed using graphical methods to further assess training effects that occur overtime.

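### The plan names a repeated measures ANCOVA with no rule for missing visits; fitted conventionally, it would discard collected week-6 or week-12 data for the outcomes measured three times.

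*Combined protocol and SAP*

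**What the plan says.** The Statistical Plan names one inferential method: "A repeated measures ANCOVA will be used to examine primary (strength) and secondary outcome measures", "for the three time points". It adds Bonferroni-corrected post-hoc analyses and, if needed, the number of training sessions completed as a covariate. It gives no estimation method, covariance structure, analysis set or rule for missing visits.

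The opening of Study Design and Methods sets two schedules. Three-visit outcomes are "Muscle Strength Testing (Baseline and Weeks 6 and 12" and "Pain and Health Surveys (Baseline and Weeks 6, and 12". Two-visit outcomes are "Functional Testing (Baseline and Week 12" and, from the secondary outcomes under Hypothesis 1, "Increased peak power and average power output at 12 weeks compared to baseline".

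Hypothesis 1 compares both week 6 and week 12 with baseline for strength (the primary outcome), pain and SF-36 WW. The week-6 change is therefore a stated contrast in its own right.

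Two rules can end follow-up early. Under Visit 3: "If a subject completes less than 10 exercise sessions in a 6-week period they will be removed from the study". In the training-phase text: "Any subject reporting or testing positive for pregnancy will be withdrawn from the study".

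**The concern.** A classical repeated measures analysis treats the subject's set of visits as the unit, so a subject with one empty visit cannot enter. The protocol can itself produce such subjects. The attendance rule is applied per six-week period, so it can remove someone in the second period who already has baseline and week-6 measurements. Pregnancy withdrawal can also fall after week 6. The two-week visit windows accommodate late visits but not missed ones.

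Two things are at stake. The first is waste: a stated primary contrast, week 6 against baseline, would be estimated without subjects in whom it was fully observed. The second is selection: the analysis would describe completers, and Hypothesis 1 rests on change over time with no control comparison that might offset this. Leaving the point open also means that the set of subjects analysed could be settled after the data are seen.

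**Working it through.** The plan states no sample size, power, SD, effect size or dropout rate, so there is no figure of its own to reproduce. All numerical inputs below are assumptions.

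**1. Does the conventional analysis need complete rows?** Twenty simulated subjects with three visits each, less one week-12 value, leave 59 observations. A classical repeated measures ANOVA routine rejected these data as unbalanced. A mixed model used all 59.

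**2. How much is discarded?** If k of N subjects have baseline and week 6 but not week 12, complete-case analysis discards 2k of the 3N − k values collected for each outcome.
- N = 20, 20% lost: k = 4, so 8 of 56 values.
- N = 24, 25% lost: k = 6, so 12 of 66 values.

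**3. Precision of the week-6 gain.** Take each visit's SD as 1 and the baseline to week-6 correlation as 0.8.
- Variance of the change = 2(1 − 0.8) = 0.4, so its SD = 0.632.
- All 24 observed pairs: SE = 0.632/√24 = 0.129.
- 18 completers: SE = 0.632/√18 = 0.149. The ratio is √(24/18) = 1.155.
- If the number lost varies at random around 25%, the simulated SE is up to 0.151, a ratio of 0.151/0.129 = 1.17.
- For other loss rates the ratio is 1/√(1 − loss): 1.05, 1.12 and 1.20 at 10, 20 and 30%.

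**4. Bias if loss after week 6 depends on early gain.** Assume true gains of 0.30 SD (week 6) and 0.50 SD (week 12), and correlations of 0.8 (baseline, week 6), 0.8 (week 6, week 12) and 0.7 (baseline, week 12).
- Covariance of the two gains = 0.8 − 0.7 − 0.8 + 1 = 0.3. The week-12 bias is therefore 0.3/0.4 = 0.75 of the week-6 bias.
- Let logit P(lost) = a − g·z, where z is the standardised week-6 gain and a is set so that 25% are lost. Let m be the mean of z among completers. The expected complete-case gains are 0.30 + 0.632m and 0.50 + 0.75 × 0.632m.
- g = 0 (loss at random): m = 0, giving 0.30 and 0.50.
- g = 0.5: m = 0.120, giving 0.38 and 0.56.
- g = 1: m = 0.213, giving 0.43 and 0.60.
- g = 2: m = 0.319, giving 0.50 and 0.65.

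Simulation of the same scenario gave about 0.37-0.50 and 0.56-0.65.

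**5. Sensitivity to the assumptions.** With equal correlations of 0.7 to 0.9, 10 to 30% lost and g = 1, the complete-case gains are 0.34-0.50 SD at week 6 and 0.52-0.60 SD at week 12. An estimate using all observed data stays at about 0.30 and 0.50. That follows from the set-up, because loss was made to depend only on observed values.

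**The case against.** The strongest reply is that the plan nowhere says incomplete subjects are dropped. That is correct. The label can cover a model fitted to all available visits, and the post-hoc comparisons, if run as paired contrasts, could keep anyone with the relevant pair. A reader might infer that the plan deletes these subjects; the documents support only that the conventional fit would, and that nothing written prevents it.

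Three further inferences should also be resisted.
- **That every outcome is affected.** Propulsion, transfer and power have no week-6 measurement, so there is no week-6 value to lose. A subject removed in the first six weeks may have none either.
- **That the gains will be biased upward.** The protocol gives scheduling conflicts and illness as reasons for changed visits, and no stated link ties pregnancy withdrawal to strength gain. A pain-related halt stops training, not a test visit. A link between loss and early gain is plausible, because removal depends on attendance and a halt can lower it, but it is not documented. Without such a link only precision is lost.
- **That the F test has a materially inflated type I error through non-sphericity.** The plan does not say that the test is uncorrected. At the correlations assumed here epsilon is 0.92, and the simulated error is about 5.4-5.5% for a nominal 5%. This adds nothing to the point.

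The study is also described as exploratory, which limits how much weight the point should carry. What stands is that a method which conventionally needs complete rows is named alongside rules that can create incomplete ones, with nothing to connect them.

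**Conclusion.** The point holds for the three-visit outcomes: strength, NRS, WUSPI and SF-36 WW. Under the conventional fit, subjects lost after week 6 and subjects missing only week 6 would be excluded from contrasts for which their data exist.

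A loss of precision is certain whenever such subjects exist: about 15-17% on the SE of the week-6 gain at an assumed 25% loss. Bias is conditional on loss being related to early gain. In the assumed scenario it adds roughly 0.07-0.20 SD at week 6 and 0.06-0.15 SD at week 12. These sizes rest on assumed numbers, loss rates, correlations and dependence, and none can be derived from the documents. The plan should be changed because a better method is available at almost no cost, not because any particular bias has been shown.

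**What to change.** For strength, NRS, WUSPI and SF-36 WW, replace the ANCOVA sentence with wording such as: a likelihood-based mixed model for repeated measures, with visit (baseline, week 6, week 12) as a categorical factor and an unstructured covariance, will be fitted to all observed visits of every subject with a baseline, including subjects later removed or withdrawn; week 6 minus baseline and week 12 minus baseline will be estimated as contrasts with their own standard errors. Name a simpler covariance in advance in case the unstructured one does not converge. State whether the sessions-completed covariate enters this model. Keep the complete-case ANCOVA as a sensitivity analysis.

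For propulsion, transfer and power, specify the baseline to week-12 change.

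The cost is analysis-plan wording only; no visit or procedure changes. The model relies on data being missing at random given the observed visits. It would not remove bias if loss depended on the unobserved week-12 value itself.
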